8.5.3 Reporting of Pregnancy Cases Occurring During the Clinical Study

National regulations require that the Sponsor collect information on pregnancies occurring during clinical trials, in which exposure to the study drug at any time during pregnancy, via either maternal or paternal exposure, is suspected.

Therefore, pregnancy and suspected pregnancy (including a positive pregnancy test regardless of age or disease state) of a female patient or the female partner of a male patient occurring while the patient is on study drug, or within 31 days of the patient’s discontinuation visit, are considered an immediately reportable events.

The investigator will report the following events immediately and always within 24 hours from first knowledge:

- Any occurrence of a pregnancy where any kind of exposure to the study drug is suspected.
- Possible exposure of a pregnant woman.
- All reports of elevated/questionable or indeterminate beta human chorionic gonadotropins (β -hCGs).

Immediately after detecting a case of suspected pregnancy in a female clinical trial patient, the decision on her continued participation in the clinical trial will be jointly taken by the trial patient, the Investigator and the Sponsor with the patient’s best interest in mind. A decision to continue the pregnancy will require immediate withdrawal from the trial.

Any pregnancy, suspected pregnancy, or positive pregnancy test must be reported to the Pharmacovigilance Department at PharmaMar immediately by facsimile using the Pregnancy Report Form.

The Investigator will follow the pregnancy until completion/termination, and must notify the outcome of the pregnancy to the Pharmacovigilance Department at PharmaMar within 24 hours of first knowledge as a follow-up to the initial Pregnancy report.

For any event during the pregnancy which meets a seriousness criterion (including fetal or neonatal death or congenital anomaly), the Investigator will also follow the procedures for reporting SAEs (complete and send the SAE form to Sponsor, Pharmacovigilance by facsimile within 24 h of the Investigator’s knowledge of the event).

All neonatal deaths that occur within 30 days of birth should be reported, regardless of causality, as SAEs. In addition, any infant death at any time thereafter that the Investigator suspects as related to the in utero exposure to the study drug should also be reported to the Pharmacovigilance Department at PharmaMar by facsimile within 24 h of the Investigators' knowledge of the event.

8.6 ADVERSE EVENTS MONITORING

Safety review will be performed at Pharma Mar, S.A. once the SAE forms have been received and the eCRFs have been completed by the Investigator.

Periodic safety review of clinical data will be performed; however, no formal Data Safety Monitoring Board has been appointed for this trial. AEs will be monitored by the Investigators and by the study team at Pharma Mar, S.A. The personnel in charge of this process are defined in the section "Study Contacts" of this protocol. In general, a clinical oncologist, together with a member of the Pharma Mar, S.A. Pharmacovigilance Department will review the safety data of this trial on an ongoing basis.

- SAEs will be collected, assessed and reported as per the applicable Regulations by the Pharmacovigilance Department.

Non-serious AEs will be checked for accuracy against the eCRF during monitoring visits by the monitor.

8.7 EFFICACY

Not applicable.

9. STATISTICAL METHODS

This clinical pharmacology study is designed to assess the impact of bosentan co-administration on lubrinezetin PK parameters administered alone.

9.1 ANALYSIS POPULATIONS

The PK population will include all patients enrolled who have sufficient and interpretable PK parameters to calculate the non-compartmental PK parameters. Only the patients who have completed the two cycles and have sufficient and interpretable PK assessments will be included in the statistical comparison to assess the effect of bosentan on the PK of lubrinezetin.

The safety population will include all patients who received at least one dose of lubrinezetin. Patients who have received at least one dose of bosentan but who did not receive any dose of lubrinezetin will be excluded from the safety population. The analysis of data from these patients will be performed separately (e.g., by means of narratives). The safety population will be used for all safety evaluations.

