EXPECTED NUMBER OF PATIENTS	Eight patients will be enrolled. Additional patient(s) may be enrolled if any patient(s) does not complete the required assessments, including the PK blood sample collections of the first and second cycles.
REPLACEMENT OF PATIENTS	
Patients must be replaced if they are not evaluable for the assessment of the primary endpoint (e.g., if they have not sufficient and interpretable PK parameters).
 
All replaced patients who received the study treatment will be included in the general safety analysis.

STUDY DRUGS FORMULATION	
Bosentan: Commercially available bosentan film-coated tablets (with strengths of 125 mg) will be provided by the Sponsor.
 
Lurbinectedin: Lurbinectedin 4 mg drug product (DP) is presented as a lyophilized powder for concentrate for solution for infusion in 30 mL vials and will be supplied by the Sponsor for the purposes of this study. Before use, the 4 mg DP should be reconstituted with 8 mL of water for injection to give a solution containing 0.5 mg/mL of lurbinectedin. For administration to patients as an i.v. infusion, reconstituted vials are diluted with glucose 50 mg/mL (5%) solution for infusion or sodium chloride 9 mg/mL (0.9%) solution for infusion. The full composition of the lurbinectedin 4 mg DP and the reconstituted solution per mL is shown in Table S1.
 
Table S1. Composition of lurbinectedin (PM01183) vials.
 
  
 Component	Concentration/vial	Concentration/vial after reconstitution	
   
 Lurbinectedin	4.0 mg	0.5 mg/mL	
 
 Sucrose	800 mg	100 mg/mL	
 
 Lactic acid	22.08 mg	2.76 mg/mL	
 
 Sodium hydroxide	5.12 mg	0.64 mg/mL	
  
	Component	Concentration/vial	Concentration/vial after reconstitution	Lurbinectedin	4.0 mg	0.5 mg/mL	Sucrose	800 mg	100 mg/mL	Lactic acid	22.08 mg	2.76 mg/mL	Sodium hydroxide	5.12 mg	0.64 mg/mL
Component	Concentration/vial	Concentration/vial after reconstitution														
Lurbinectedin	4.0 mg	0.5 mg/mL														
Sucrose	800 mg	100 mg/mL														
Lactic acid	22.08 mg	2.76 mg/mL														
Sodium hydroxide	5.12 mg	0.64 mg/mL														

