*** Permitted windows for assessments before Day 1 of Cycle 1:**

If physical examination, ECOG PS, vital signs, Hematology, Biochemistry-A, Biochemistry-B, CLcr (provided only if serum creatinine levels are above ULN) and Coagulation were assessed >10 days before Day 1 of Cycle 1, the tests must be repeated the day before or the Day 1 (always prior to lubrinezdin infusion).

If pregnancy test was done >7 days before Day 1 of Cycle 1, the test must be repeated the day before or the Day 1 (always prior to lubrinezdin infusion).

A patient should only be treated if eligibility criteria are still met according to assessments performed closest to treatment start.

Permitted windows for assessments after Day 1 of Cycle 1:

A ± 2 -day time window will be allowed for Hematology, Biochemistry-A and CLcr (provided only if serum creatinine levels are above ULN) on Day 8 and Day 15, and for vital signs on Day 8 of Cycle 1.

A -1 day window will be allowed for physical examination, ECOG PS, vital signs, Hematology, Biochemistry-A, and Biochemistry-B, CLcr (provided only if serum creatinine levels are above ULN) and Pregnancy test on Day 1 of Cycle 2 and further cycles (always prior to lubrinezdin infusion).

A $+2$ days window for Day 1 lubrinezdin administration of Cycle 3.

If a drug administration is delayed beyond the permitted protocol window, assessments planned for the original administration day must be repeated on the day the dose is finally administered.

^a Should treatment be administered more than ten days after the screening tests, repeat these tests prior to the first infusion and if clinically indicated. Height needs to be measured at baseline only. BSA will not be reported at the EOT. BSA calculated according to DuBois formula (see [Appendix 4](#)).

^b Any patient having any grade ≥ 3 laboratory abnormalities and/or treatment-related AEs is suggested to have the relevant tests re-assessed at intervals of at least 72 hours but not more than one week until recovery to at least grade 2 has been documented.

^c Repeat during treatment period and at EOT if clinically indicated.

^d Calculated CLcr [Cockcroft and Gault's formula] should be provided only if serum creatinine levels are above ULN.

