5.2 PLANNED STUDY PERIODS (INDIVIDUALLY PER PATIENT)

Patients will be evaluated at scheduled visits in three study periods:

- **Pre-treatment (screening)**: from signature of the ICF to the day of first administration of the study treatment (bosentan or lorbinectedin).
- **Treatment**: from first administration of the study treatment (bosentan or lorbinectedin) to the last dose of lorbinectedin plus 31 days (end-of-treatment, EOT) (maximum of three cycles).
- **Follow-up of adverse events**: after EOT, patients with treatment-related toxicities $>$ grade 2 will be followed every four weeks until recovery to at least grade 1 or stabilization of all treatment-emergent AEs, or until the start of a new antitumor therapy, until the continuation of treatment outside this study under a Compassionate Use Agreement or death, whichever occurs first.

Patients will be considered to be **on-study** from the signature of the ICF to the end of the follow-up period. Patients will be considered to be **on-treatment** for the duration of their treatment and until the day of EOT, immediately before the start of the follow-up period.

An end-of-treatment visit will be performed within 31 days (± 10 days) after administration of the last dose of lorbinectedin, unless the patient dies or starts any new antitumor therapy outside this clinical study, in which case the EOT visit should be performed immediately before the start of the new therapy (ideally the day before or the same day).

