5.3 REPLACEMENT OF PATIENTS

Patients must be replaced if they are not evaluable for the assessment of the primary endpoint (e.g., if they have not sufficient and interpretable PK parameters).

Evaluable patients for the main objective of the study (e.g., assessment of lurbinectedin PK) should have provided sufficient and interpretable PK parameters (e.g., AUC_{0-t} should cover at least 80% of $AUC_{0-\infty}$) of Cycle 1 and 2. Evaluable patients should have received the first two complete cycles regardless dose delays or reductions.

The compliance of bosentan will be confirmed based on a patient's diary, the drug accountability and the expected individual plasma concentration at the steady state.

Any replacement subject during the treatment phase will be given a new subject number and assigned to the same sequence as the not-evaluable subject being replaced. All replaced patients who received the study treatment will be included in the general safety.

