3 PATIENTS EVALUABILITY CRITERIA

Patients must fulfill all the inclusion/exclusion criteria to be enrolled in the study.

The study will include the following analysis population set definitions:

- The enrolled population is defined as all patients recorded in the database who have been included in the trial and randomized, regardless of whether they have received the study drug or not. Screening failure patients will not be considered as part of this population.
- The PK population will include all patients who have provided sufficient and interpretable PK parameters to calculate the non-compartmental PK parameters. Evaluable patients should have received the first two complete cycles regardless dose delays or reductions.
- The safety population will include all patients who received at least one dose of lorbinecetin. Patients who have received at least one dose of bosentan but who did not receive any dose of lorbinecetin will be excluded from the safety population and will be performed separately by narratives. The safety population will be used for all safety evaluations.

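### Patients who take bosentan but never reach the infusion are left out of the safety population, against the replacement rule, and this can happen only in Sequence 1

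*Protocol*

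**What the plan says.** **Safety population.** Protocol 9.1 requires at least one dose of lurbinectedin. It then places outside the population "Patients who have received at least one dose of bosentan but who did not receive any dose of" that drug, and adds: "The analysis of data from these patients will be performed separately (e.g., by means of narratives"). It also states: "The safety population will be used for all safety evaluations". The synopsis (Statistical methods, Analysis populations) has the same rule. In SAP 3 these patients "will be excluded from the safety population and will be performed separately by narratives". Protocol 3.4.2 and 8.3, the safety item under the synopsis secondary endpoints, and SAP 4.2.2 also tie safety evaluability to at least part of a lurbinectedin infusion.

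**Replacement rule.** Synopsis, Replacement of patients: "All replaced patients who received the study treatment will be included in the general safety analysis". Protocol 5.3: "All replaced patients who received the study treatment will be included in the general safety". Protocol 5.2 starts the treatment period at the "first administration of the study treatment (bosentan or" lurbinectedin). The synopsis (Planned trial periods) and the Table 5 footnote on the on-treatment period say the same.

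**Timing.** Under Protocol 7.2, Sequence 1 takes bosentan from Day -5 of Cycle 1, before any lurbinectedin. Sequence 2 takes it from Day -5 of Cycle 2, after the Cycle 1 infusion. The Sequence 1 schedule adds: "A patient should only be treated if eligibility criteria are still met according to assessments performed closest to treatment start".

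**The concern.** Membership of the safety population depends on something that happens after study treatment has begun. In Sequence 1, an adverse event during the five lead-in days, or a repeat laboratory value out of range on Day 1, can stop the first infusion. The patient then falls outside the population because of what happened on bosentan. Such a patient has no lurbinectedin PK and must be replaced, so Protocol 5.3 puts the patient into the safety analysis and 9.1 takes the patient out.

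The rule is also one-sided: the same event in Sequence 2 leaves the patient in the population. At stake are the bosentan-related tables (SAP 11.2.1.4 for adverse events, 11.3.1.3 for serious adverse events) and the by-sequence tables, where one patient among about eight changes the picture.

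**Working it through.** The plan gives no figure on this point, so the check is mainly one of passages.

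**Step 1. One patient, two answers.** Take a Sequence 1 patient who takes bosentan from Day -5, has an event on Day -1 and is not infused.

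| Rule | Result for this patient |
|---|---|
| Synopsis (replacement) and Protocol 5.3, with study treatment as in 5.2 | Must be replaced; in the general safety analysis |
| Synopsis (analysis populations), Protocol 9.1, SAP 3 | Outside the safety population; narrative |

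**Step 2. Only in one sequence.** A Sequence 2 patient who stops in the Cycle 2 lead-in received lurbinectedin in Cycle 1 and so meets the definition in 9.1. A bosentan-only patient can therefore come only from Sequence 1.

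**Step 3. Which outputs are affected.** SAP 11 runs the safety analysis on the safety population. The patient is therefore absent from Tables 11.2.1.4 and 11.3.1.3 and from the by-sequence tables 11.2.1.5, 11.2.1.7, 11.3.1.4 and 11.3.1.6. SAP 10.1 runs the disposition outputs on the enrolled population, so the stop appears there, including in the listings of discontinuation due to adverse events. The data listings in SAP Appendices IV to VI name no population and may also show the event.

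**Step 4. Size, as an illustration.** Inputs from the documents: 8 planned patients and 1:1 allocation, hence 4 per sequence. Assumption: x Sequence 1 patients stop in the lead-in with a bosentan-related event, each is replaced, and nobody else has such an event. The current rule shows 0/8 whatever x is. With all bosentan-exposed patients counted, the proportion is x/(8 + x) overall and x/(4 + x) in Sequence 1.

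| x | All bosentan-exposed | Sequence 1 |
|---|---|---|
| 0 | 0/8 (0%) | 0/4 (0%) |
| 1 | 1/9 (11%) | 1/5 (20%) |
| 2 | 2/10 (20%) | 2/6 (33%) |
| 3 | 3/11 (27%) | 3/7 (43%) |

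Exact (Clopper-Pearson) 95% limits for 1/9: the lower limit is 1 - 0.975^(1/9) = 0.3%, and the upper limit solves P(X ≤ 1 | 9, p) = 0.025, giving 48%. For 0/8 the upper limit is 1 - 0.025^(1/8) = 36.9%.

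**Step 5. How likely is x ≥ 1?** The documents give no lead-in stop rate. For an assumed rate p, the chance that at least one of the first four Sequence 1 starters is affected is 1 - (1 - p)^4: 8%, 19%, 34% and 59% for p = 2%, 5%, 10% and 20%.

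**Step 6. Would the event be recorded?** Protocol 8.5.1, footnote o of both schedules and the Table 5 footnote on the AE form reserve that form for events after the first drug infusion or related to a study procedure. Protocol 9.3.2 opens the treatment-emergent window at the first dose of study drug. Footnote n of the Sequence 1 schedule limits SAE-only collection to the time up to Day -5, which suggests that lead-in events were meant to be captured. Taken literally, the form's trigger may leave a non-serious lead-in event in Sequence 1 off the AE form, even in a patient who is later infused.

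**The case against.** The exclusion is deliberate, disclosed and repeated consistently. The safety objective is the effect of bosentan on the safety profile of lurbinectedin, and a patient without lurbinectedin cannot inform it. For one patient a narrative may tell more than a table row. The SAP does not repeat the replacement rule, so its own population is unambiguous for programming. One clause in Protocol 5.3 would remove the contradiction without redefining anything.

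Part of this stands. Bosentan-only patients should stay out of lurbinectedin-related rows. It does not explain why the SAP plans bosentan-related tables that omit some bosentan-exposed patients, or why the omission falls on one sequence. A narrative does not restore numerators, denominators or worst grades.

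Three stronger readings are tempting, and the documents do not support them:

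- That the toxicity vanishes from the report. Narratives are planned, SAEs are collected from consent, and disposition uses the enrolled population.
- That data are lost for half the patients. Half is only the share allocated to Sequence 1; the rule touches those who stop before the first infusion, possibly nobody.
- That bosentan toxicity is understated by 50% at any event rate. This could apply only to events that stop treatment in the lead-in, and only under equal risk in both sequences. Sequence 2 patients reach their lead-in after Cycle 1 and a Day 15 check, so equal risk is an assumption.

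One further limit: a Sequence 2 lead-in stopper stays in the safety population, but the SAP does not say whether that patient counts under the BOS+LRB column.

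**Conclusion.** The contradiction between the replacement rule and the population definition is real, and the exclusion is one-sided by design. Any Sequence 1 patient whose lead-in event prevents the first infusion is absent from the bosentan-related and by-sequence safety tables. The effect is conditional: nothing is lost if nobody stops, and with one replaced patient it is 0/8 against 1/9 (11%). That comparison assumes a single bosentan-related event, no other replacements, and that the event is recorded as an adverse event, which the AE-form rule does not now assure. The point should be settled before the safety tables are produced. It does not touch the primary PK comparison.

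**What to change.** 1. Define the safety population as at least one dose of bosentan or lurbinectedin. Change Protocol 9.1, both synopsis passages (safety endpoint and analysis populations), Protocol 3.4.2 and 8.3, and SAP 3 and 4.2.2 together. The synopsis replacement rule and Protocol 5.3 then agree and need only spell out that study treatment means either drug.
2. Use all bosentan-exposed patients, including Sequence 2 patients who stop in the Cycle 2 lead-in, as the denominator for Tables 11.2.1.4 and 11.3.1.3. Label the columns to show that some received bosentan only.
3. Include these patients in the by-sequence AE and SAE tables.
4. Keep a lurbinectedin-treated flag for the lurbinectedin-related, exposure, delay and reduction tables. Keep the narratives as well.
5. Reconcile the AE-form trigger (Protocol 8.5.1, schedule footnote o, the Table 5 footnote) with the treatment-emergent window in 9.3.2 and with schedule footnote n, so that Sequence 1 lead-in events are recorded as adverse events. Without this, the wider population would not bring non-serious lead-in events into the tables.

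The cost is wording in both documents, one population flag, column labels and a revised AE-form instruction. The small downside is that denominators differ between tables. Limiting Protocol 5.3 to lurbinectedin-treated patients would be cheaper and would end the contradiction, but it would leave the one-sided omission in place.

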9.2 SAMPLE SIZE

A block randomization (1:1 ratio) will be performed. At least 8 patients are expected to complete all study procedures, including the collection of sufficient and interpretable PK assessments. Although at least 8 patients will be enrolled in this study; it is estimated that complete data from eight patients will be sufficient to estimate the drug-

drug interaction of bosentan on the PK of lurbinecetin. In case of patient replacement, a new patient number will be provided and he/she will be assigned to the same sequence as the patient being replaced.

This study was designed to assess the potential effects of bosentan on the PK of lurbinecetin in patients with advanced malignancies. The 90% CI will be used to help with the interpretation of the results. A sample size of eight patients was based on feasibility and clinical considerations. Based on previous studies, the intra-subject coefficient of variation (CV) of lurbinecetin PK parameters is estimated to be more than 30%. The precision (half-width) of the 90% CI for [(lurbinecetin + bosentan) / lurbinecetin alone] comparison on the log-scale will extend 0.389 from the observed differences in means, assuming that the intra-subject CV around 40%. This half-width corresponds to a 90% CI in the range of 70% and 147% assuming the ratio of the means equal to unity for each PK parameter. This 90% CI will be used to help with the interpretation of the results.

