3. OVERALL STUDY DESIGN

3.1 STUDY DESIGN

This is a prospective, open-label, two-way crossover, phase Ib drug-drug interaction study in patients with advanced solid tumors.

The study will include a pre-treatment (screening) phase followed by a treatment phase consisting of two lorbinecetin cycles, one cycle in combination with bosentan and one cycle of lorbinecetin as single agent (in different order depending on the study sequence), and one additional third cycle of lorbinecetin as a single agent for patients who meet the continuation criteria and obtain a clinical benefit after the first two cycles, and then follow-up of adverse events if any.

Patients who meet the continuation criteria and obtain a clinical benefit after the first two cycles according to the Investigator's criteria will have the opportunity to continue treatment under a Compassionate Use Agreement after the completion of the optional third study cycle.

Patients will be treated as outpatients. At the discretion of the Investigator, patients may be admitted to the study center on Day -1 or Day 1 and monitored, at least, until completion of the Day 1 PK blood sample collections.

Patients will receive a maximum of three cycles: two consecutive cycles of lorbinecetin, one cycle with and one cycle without bosentan co-administration (in different order depending on the study Sequence 1 or Sequence 2 of treatment), followed by a third cycle with lorbinecetin alone (this last optional for patients with clinical benefit). Lorbinecetin will be administered as a 1-hour (-5/+20 min) i.v. infusion q3wk via a central or peripheral vein.

[figure not shown]
In the co-administration cycles, bosentan will be administered orally twice daily in the morning and evening during the prior five consecutive days, self-administered at home from Day -5 to Day -1 (i.e., five days before lorbinecetin infusion), and once daily on

Day 1 (i.e., the day of lorbrena infusion), following recommendations at the Summary of Product Characteristics (SmPC). On Day 1 (i.e., the day of lorbrena infusion), bosentan will be given immediately prior to starting the lorbrena infusion. In fact, bosentan should be administered after obtaining the bosentan pharmacokinetic (PK) sample #1 and before the start of lorbrena infusion (-15 min to -1 min).

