9.3.4 Pharmacokinetics

Plasma exposure to lurbinecetin

Only patients who completed the study with sufficient and interpretable PK parameters will be included in the statistical comparison of plasma exposure to lurbinecetin.

Descriptive statistics will be used to summarize pharmacokinetic data.

The primary parameter of interest for the statistical analysis will be plasma dose-adjusted $AUC_{(0-\infty)}$ (if data do not permit so, $AUC_{(0-t)}$ will be used) of lurbinecetin. The

analysis will compare the log-transformed AUC for lubrinedin administered in combination with bosentan (Test) to the lubrinedin alone (Reference).

A mixed-effects model will be fit to the data with log-transformed AUC as the dependent variable, treatment (Test or Reference), period and sequence as fixed effects, and patient (sequence) as a random effect. The estimated least square means and intrasubject variability from the mixed-effects model will be used to construct 90% CIs for the difference in means on the log scale between treatments (Test or Reference). The adjusted mean differences and the 90% CIs will be exponentiated to obtain estimates of the ratio of adjusted geometric means (Test/Reference) and 90% CIs for the ratios.

A large difference (e.g. two-fold difference shown from CIs and least square means) will be considered to show evidence on whether bosentan co-administration has a clinically relevant effect on lubrinedin exposure.

Secondary PK parameters

Similar models used for the primary endpoint will be fit to the data with dose-normalized $AUC_{(0-t)}$ and C_{max} and in C_l , V_{ss} and $T_{1/2}$ of lubrinedin or metabolite to parent exposure PK parameters ratio, as the dependent variable. Results will also be assessed graphically.

Plasma protein binding

A similar model used for the primary endpoint will be fit to the data with dose-normalized AUC_u as the dependent variable.

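### The stated 90% CI half-width of 0.389 does not follow from an intra-subject CV of 40%, which gives 0.374 (69% to 145%), and the printed 70% lower limit follows from neither figure

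*Protocol*

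**What the plan says.** Protocol section 9.2 gives one precision statement. "The precision (half-width) of the 90% CI for" the comparison of lurbinectedin plus bosentan with lurbinectedin alone, on the log scale, "will extend 0.389 from the observed differences in means, assuming that the intra-subject CV around 40" percent. It then converts this half-width to an interval of 70% to 147%, "assuming the ratio of the means equal to unity for each PK parameter". The synopsis and SAP section 5.2 carry the same figures.

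On where the number of patients comes from, section 9.2 is explicit: "A sample size of eight patients was based on feasibility and clinical considerations". It also says that earlier studies put the intra-subject CV above 30%.

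The design is a two-way crossover with 1:1 allocation to the two sequences. Section 9.3.4 specifies a mixed model for log-transformed AUC with "treatment (Test or Reference), period and sequence as fixed effects, and patient (sequence) as a random effect", and exponentiates the result to a ratio of geometric means with its 90% CI.

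Neither document shows the formula behind 0.389, its degrees of freedom, or how the CV was turned into a log-scale SD. SAP section 6 assigns the PK analysis plan to a separate document, which is not available here.

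**The concern.** A CV and a log-scale SD are different quantities. For log-normal data, which the analysis in section 9.3.4 presupposes, the SD of the logged values is sqrt(ln(1 + CV²)), and this is smaller than the CV. A half-width printed to three decimals should be recoverable from the stated CV, sample size and model. This one is not, and the lower limit of the accompanying interval does not follow from the half-width beside it.

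What is at stake is modest. This is the plan's only numerical statement of the precision to expect, and the protocol says the 90% CI will help in interpreting the results. A reader who compares achieved with planned precision should have a benchmark that agrees with its own assumption.

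**Working it through.** **Inputs**
- Confidence level: 90%, two-sided, so 5% in each tail (Protocol 9.2).
- Evaluable patients: n = 8, allocated 1:1, taken as four per sequence (Protocol 9.2).
- Design and model: two-period, two-sequence crossover (Protocol 3.1) with treatment, period and sequence fixed and patient within sequence random (Protocol 9.3.4). With eight complete pairs the residual degrees of freedom are 8 − 2 = 6.
- Intra-subject CV: about 40% (Protocol 9.2).
- True ratio: 1 (Protocol 9.2).

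**Formula**

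Half-width = t(0.95, 6) × σ × sqrt(2/8), where σ is the within-patient SD on the log scale, t(0.95, 6) = 1.9432 and sqrt(2/8) = 0.5.

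**Reproducing the plan's figure**

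With σ = 0.40: 1.9432 × 0.40 × 0.5 = 0.3886, which rounds to 0.389.

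The alternatives tried were the normal quantile; t with 5, 7 and 14 degrees of freedom; seven patients; a standard error of σ × sqrt(1/8); and a parallel 4 + 4 layout. Each was run with σ = 0.40 and with the log-normal conversion. Only σ = 0.40 with 6 degrees of freedom and n = 8 rounds to 0.389. The closest alternative with n = 8 and the converted SD uses 5 degrees of freedom and gives 0.388, but the stated model has 6.

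**The figure that a CV of 40% gives**

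σ = sqrt(ln(1 + 0.40²)) = sqrt(ln 1.16) = 0.3853.

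Half-width = 1.9432 × 0.3853 × 0.5 = 0.3743.

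exp(−0.3743) = 0.688 and exp(0.3743) = 1.454, so 69% to 145%.

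**Size of the gap**

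0.3886 − 0.3743 = 0.0143, and 0.3886/0.3743 = 1.038, an overstatement of 3.8%. Working back from 0.389: σ = 0.389/(1.9432 × 0.5) = 0.4004, and CV = sqrt(exp(0.4004²) − 1) = 41.7%.

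**The printed limits**

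| Half-width | Lower limit | Upper limit |
|---|---|---|
| 0.389, as printed | 67.8% | 147.6% |
| 0.3743, from CV 40% | 68.8% | 145.4% |
| Plan's printed range | 70% | 147% |

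The printed upper limit agrees with 0.389 to within rounding. The lower limit does not: 70% would need a half-width of ln(1/0.70) = 0.357. An interval centred on a ratio of 1 on the log scale has limits that multiply to 1, but 0.70 × 1.47 = 1.029.

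**How much the assumed CV itself matters**

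| CV | σ | Half-width | Range around 1 |
|---|---|---|---|
| 30% | 0.294 | 0.285 | 75% to 133% |
| 40% | 0.385 | 0.374 | 69% to 145% |
| 45% | 0.429 | 0.417 | 66% to 152% |
| 50% | 0.472 | 0.459 | 63% to 158% |

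**Wording of the half-width**

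0.374 is the half-width when the SD observed in the trial equals the assumed 0.385. With 6 degrees of freedom the mean of the estimated SD is 0.959σ, so the average half-width over repeated trials would be about 0.959 × 0.374 = 0.359. The figure should therefore be described as conditional on the assumed SD. It is neither a fixed result nor an expected value.

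**The case against.** The strongest reply is that the CV is only a loose planning value: the text says above 30% and around 40%. A CV of 41.7% reproduces 0.389 with the proper conversion, and using the CV as an approximate log-scale SD is common. The error is also conservative, since the plan promises slightly less precision than its assumption implies. Section 9.3.4 gives a two-fold difference as its example of a large effect, which is ln 2 = 0.693 on the log scale, so a shift of 0.014 changes no interpretation. No analysis or decision rule uses 0.389.

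Most of this stands, and it limits the point to a correction of wording. It does not make the three printed numbers agree. A half-width given to three decimals beside a CV of 40% invites checking, and the approximation is not declared. The slack in the CV does not rescue the 70% limit either, because that limit fails against the plan's own 0.389 without any inference about how 0.389 was obtained.

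A reader might go further and infer that the choice of eight patients rests on a miscalculation. The documents do not support that. Section 9.2 says the number came from feasibility and clinical considerations, so the half-width describes a sample size that was already fixed. Nor can one state as fact that the CV was entered as the SD. The match is exact and was the only one among the variants tried, but it remains an inference.

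**Conclusion.** The point holds as a minor inconsistency. With eight complete patients, 6 residual degrees of freedom and log-normal within-patient variation, a CV of 40% gives a half-width of 0.374 and a range of 69% to 145%. The plan prints 0.389 and 70% to 147%. The half-width is about 4% too wide for its stated assumption, probably because 0.40 was used as the log-scale SD, and the 70% limit is wrong under either reading.

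The consequence is small. The error is conservative, and the uncertainty in the CV moves the half-width far more than the conversion does. The sample size, design and analysis model do not change. It would be wrong to read this as evidence that the trial is too small or that its precision has been oversold.

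**What to change.** Make the same correction in the synopsis, Protocol section 9.2 and SAP section 5.2. Either option is sufficient.

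- **Keep the CV of 40%.** State that, assuming an intra-subject CV of 40% (log-scale SD 0.385), the half-width is about 0.374 if the observed SD equals the assumed SD, i.e. 69% to 145% around a ratio of 1.
- **Keep 0.389.** State the assumption as a log-scale SD of 0.40 (CV about 42%), with the same condition on the observed SD, and correct the range to 68% to 148%. Changing the assumption alone would leave the 70% limit wrong.

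In either case, add the formula and the 6 degrees of freedom so that the figure can be reproduced. The cost is a few words in three places.
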